8.3.2 Method of Detecting AEs and SAEs

Individual diary cards, specifically designed for this study by the Sponsor and provided to the study sites, will be given to study participants for the recording of daily safety information. These diary cards will include pre-listed terms and intensity scales as well as areas for free text to capture additional safety information or other relevant details. Participants will also be provided with rulers for measuring the size of injection site reactions, and with standard digital thermometers for measuring daily temperatures. To ensure consistency of reporting, the study sites will instruct participants on how to correctly use these tools.

At specified intervals, the Investigator or an authorized designee will interview the participants to collect the information recorded in the diary card, and will attempt to clarify anything that is incomplete or unclear. All clinical study information gathered by the study site will be reported electronically by the Investigator or authorized designee using a web-based CRF. Any information that was not documented in the diary card will first be captured in the source document and then reported electronically.

The 6-month follow-up will be done by interviewing participants over the telephone using a questionnaire to capture SAEs and AESIs, if applicable.

The method of recording, evaluating, and assessing causal relationship of AE and SAE and the procedures for completing and transmitting SAE reports are provided in [Appendix 10.3](#).

Care will be taken not to introduce bias when detecting AEs and/or SAEs. Open-ended and non-leading verbal questioning of the participant is the preferred method to inquire about AE occurrences.

8.3.3 Follow-up of AEs and SAEs

Unless a participant refuses further contact, each participant who experiences an AE (whether serious or non-serious) during the study must be followed until the condition resolves, becomes stable, or becomes chronic (even after the end of the participant's participation in the study) if *either* of the following is true:

- The AE is considered by the Investigator to be related to the study intervention administered
- The AE caused the discontinuation of the participant from the study or from vaccination

The Investigator will inform the Sponsor of the date of final disappearance of the event or the date of "chronicity" establishment.

8.3.4 Regulatory Reporting Requirements for SAEs

- Prompt notification by the investigator to the Sponsor of a SAE is essential so that legal obligations and ethical responsibilities towards the safety of participants and the safety of a study intervention under clinical investigation are met.
- The Sponsor has a legal responsibility to notify both the local regulatory authority and other regulatory agencies about the safety of a study intervention under clinical investigation. The Sponsor will comply with country-specific regulatory requirements relating to safety reporting to the regulatory authority, IRB/IEC, and investigators.
- For all studies except those investigating medical devices investigator safety reports must be prepared for suspected unexpected serious adverse reactions (SUSAR) according to local regulatory requirements and Sponsor policy and forwarded to investigators as necessary.
- An investigator who receives an investigator safety report describing a SAE or other specific safety information (eg, summary or listing of SAEs) from the Sponsor will review and then file it and will notify the IRB/IEC, if appropriate according to local requirements.

8.3.5 Pregnancy

Pregnancy is an exclusion criterion for enrollment in this study, but a participant could potentially become pregnant during her participation.

- Details of all pregnancies in female participants will be collected after the start of study intervention and until delivery by the investigator and recorded in the Pregnancy CRF. Any data collected after CRF lock will be transmitted to the pharmacovigilance department on the paper form.
- If a pregnancy is reported, the investigator should inform the Sponsor within 1 month of learning of the pregnancy and should follow the procedures outlined in [Appendix 10.4](#).
- Abnormal pregnancy outcomes (eg, spontaneous abortion, fetal death, stillbirth, congenital anomalies, ectopic pregnancy) are considered SAEs.

8.3.6 Adverse Events of Special Interest

An AESI is an event for which ongoing monitoring and rapid communication by the Investigator to the Sponsor must be done. AESI will be collected throughout the study. AESI include the following:

- Anaphylaxis defined as per the Brighton collaboration case definition [\(28\)](#).

8.4 Treatment of Overdose

Since the study intervention is administered by a health care professional, it is unlikely that overdose by injection occurs.

However, in the event of an overdose, the Investigator should:

- 1) Contact the Medical Monitor immediately.
- 2) Closely monitor the participant for any AE/SAE.
- 3) Document the quantity of the excess of the overdose in the source documents.

8.5 Pharmacokinetics

Pharmacokinetics parameters are not evaluated in this study.

8.6 Pharmacodynamics

Pharmacodynamic parameters are not evaluated in this study.

8.7 Genetics

Genetics are not evaluated in this study.

8.8 Biomarkers

No other biomarkers than those described in the immunogenicity assessments section (Section 8.1.2) are evaluated in this study.

8.9 Immunogenicity Assessments

See [Section 8.1.2](#).

8.10 Medical Resource Utilization and Health Economics

Medical Resource Utilization and Health Economics parameters are not evaluated in this study.

9 Statistical Considerations

9.1 Statistical Hypotheses

No hypotheses will be tested. The analyses will be descriptive.

9.2 Sample Size Determination

There are no statistically powered hypotheses in this study thus no formal sample size computation. The number of participants is judged sufficient to provide useful immunogenicity and safety data on the 3 SP0202 formulations, Prevnar 13 and Pneumovax 23.

The sample size was set to approximatively 150 participants per vaccine group and approximatively 75 by age group. Assuming a drop-out rate of approximatively 15%, a total of 128 participants by vaccine group (Per Protocol Analysis Set [PPAS]) are expected.

The expected precision of estimation for quantitative data is as follows (PPAS) - the maximum distance from the \log_{10} mean to the limits of 95% CI is equal to 0.173 for single mean and 0.246 for difference in means of two groups (when the standard deviation is 1).

Standard deviation	N evaluable	Distance between \log_{10} mean and 95%CI limits for a single mean	Distance between 2 groups difference in \log_{10} means and 95%CI limits	Distance between GMT and 95%CI limits for a single mean	Distance from GMT ratio between 2 groups to 95%CI upper limit
0.5	128	0.087	0.123	1.22	1.33
0.6	128	0.104	0.148	1.27	1.41
0.7	128	0.121	0.172	1.32	1.49
0.8	128	0.139	0.197	1.38	1.57
0.9	128	0.156	0.222	1.43	1.67
1	128	0.173	0.246	1.49	1.76

9.3 Populations for Analyses

The following populations are defined:

Population	Description
Randomized	All participants with data in the CRF
Safety Analysis Set (SafAS)	Participants who have received the study vaccine. All participants will have their safety analyzed according to the vaccine they actually received. Safety data recorded for a vaccine received out of the protocol design will be excluded from the analysis (and listed separately).
Full analysis set (FAS)	Subset of randomized participants who received at least 1 dose of the study vaccine and had a valid post-vaccination blood sample result. Participants will be analyzed according to the intervention to which they were randomized.

Per-protocol analysis set (PPAS)	
Subset of the FAS. Participants presenting with at least one of the following relevant protocol deviations will be excluded from the PPAS:
 
• Participant did not meet all protocol-specified inclusion criteria or met at least one of the protocol-specified exclusion criteria• Participant did not receive vaccine• Participant received a vaccine other than the one that he / she was randomized to receive• Preparation and / or administration of vaccine was not done as per-protocol• Participant did not provide the post-dose serology sample at V2 in the proper time window or a post-dose serology sample was not drawn• Participant received a protocol-prohibited therapy / medication / vaccine) 
In addition to the reasons listed above, participants will also be excluded from the PPAS if their Visit 02 / post-vaccination serology sample did not produce a valid test result (ie, results for all antigens are missing).
 
In the event of a local or national immunization program with a pandemic influenza vaccine, participants who receive 1 or more doses of a pandemic influenza vaccine at any time during the study will not be withdrawn from the study.

----------------------------------	--

9.4 Statistical Analyses

The statistical analysis plan (SAP) will be finalized prior to database lock and it will include a more technical and detailed description of the statistical analyses described in this section. This section is a summary of the planned statistical analyses of the most important endpoints.

9.4.1 General Considerations

All analyses will be descriptive.

For immunogenicity data, assuming that log10 transformation of the titers / concentrations and titers / concentrations ratio follows a normal distribution, first, the mean and 95% confidence intervals (CIs) will be calculated on log10 (titers / concentrations; titers / concentrations ratio) using the usual calculation for normal distribution, then antilog transformations will be applied to the results of calculations, to compute geometric mean titers / concentrations (GMTs / GMCs) and geometric mean of the individual titer / concentration ratios (GMTRs / GMCRs) and their 95% CIs.

The 95% CIs of ratio of GMTs / GMCs between 2 groups will be computed from the difference of log 10 transformed means of titers/concentrations using normal approximation.

The 95% CIs of point estimates will be calculated using the exact binomial distribution (Clopper-Pearson method (29)) for proportions.

Generally, no replacement of missing data will be done.

9.4.2 Safety Analyses

Safety analyses will be performed on the SafAS and presented by group and by age group for summary tables (main endpoints). The main parameters will be described with 95% CI. At least number and percentages of participants will be presented after vaccine injection reporting any:

- Immediate unsolicited systemic AEs
- Solicited injection site reactions and solicited systemic reactions occurring within 7 days after the day of injection (D1 to D8) according to presence, time of onset, intensity (Grade 1, Grade 2, or Grade 3), number of days of presence and action taken
- Unsolicited AEs occurring within 30 days after injection by system organ class (SOC) and preferred term (PT), relationship, intensity, time of onset, and duration
- All SAEs occurring throughout the study by SOC and PT, relationship and seriousness criteria
- All AESIs occurring throughout the study by SOC and PT and relationship

No replacement of missing data will be done. Nevertheless, missing relationship will be considered as related at the time of statistical analysis.

9.4.3 Immunogenicity Analyses

All immunogenicity analyses will be performed on the PPAS and presented by group and age group. Additional immunogenicity analyses will be performed on the FAS.

The point estimates and their 95% CI of at least the following parameters will be presented before and 1-month post-vaccination for each pneumococcal serotype specific OPA titers and IgG concentrations:

- GMT/GMC of serotype specific titers/concentrations
- GM of titers/ concentrations ratio (post- / pre-vaccination)

Differences in terms of ratio of GMTs/GMCs between 2 groups (ie, any SP0202 formulations and Prevnar 13 or Pneumovax 23) post-vaccination will be presented.

Reverse cumulative distribution curves (RCDCs) of individual concentrations/titers will be presented for all serotypes at pre and post-vaccination.

Missing data will not be imputed. No test or search for outliers will be performed.

For the calculation of GMTs / GMCs and percentage above cut-offs, any pre-vaccination or post-vaccination value reported as < LLOQ will be converted to a value of 0.5 LLOQ.

For the calculation of GMTR / GMCR, any pre-vaccination value reported as < LLOQ will be converted to LLOQ, and any post-vaccination value reported as < LLOQ will be converted to a titer of 0.5 LLOQ when only either the numerator or the denominator is < LLOQ. If both

numerator and denominator are < LLOQ, then both will be converted in the same way so that the increase is defined as 1.

Any value reported as > ULOQ (upper limit of quantitation) will be converted to ULOQ.

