4.3.2 Immunogenicity

4.3.2.1 Computed Values for Analysis

In order to appropriately manage extreme values (< LLOQ and \geq ULOQ (lower limit of quantitation and upper limit of quantitation, respectively)) for analysis purposes of Geometric Mean Titer (GMTs), Geometric Mean Concentration (GMCs), and thresholds the following computational rules will be applied to the values provided in the clinical database:

- If a value is < LLOQ, then the computed value is LLOQ/2
- If a value is between \geq LLOQ and < ULOQ, then the computed value is the value
- If a value is \geq ULOQ, then the computed value is ULOQ

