5.4.3 Immunogenicity Analyses

The immunogenicity analyses will be performed first on the PPAS and then on the FAS.

The point estimates and their 95% CI of the following parameters will be presented by group for all participants and by age group before and one month post-vaccination for each pneumococcal serotype specific OPA titers and IgG concentrations:

- GMT/GMC of serotype specific titers/concentrations.
- GMT/GMC ratio (post/pre-vaccination).

In addition, the following analyses will be presented:

- Differences in terms of ratio of GMTs/GMCs between 2 groups (for instance, any SP0202 formulations and Prevnar 13 or Pneumovax 23) and 95% CI at 1-month post-vaccination on all participants and by age group.
- Percentages of participants with titers/concentrations above certain thresholds and achieving several X-fold from pre to post-vaccination.
- Several graphical representations (in a log10 scale) will be used for all serotypes by group for all participants and by age group:
 - RCDCs of individual OPA titers and IgG concentrations at pre and 1-month post-vaccination.
 - Forest plots of GMTs or GMCs at pre and 1-month post-vaccination.
 - Forest plots of GMT/GMC ratio between groups at 1-month post-vaccination.
 - Boxplots of the OPA titers and IgG concentrations at pre and 1-month post-vaccination.

Table 5.2: Summary of statistical analyses for immunogenicity analysis

Endpoint	Visit and Age group	Description
Serotype-specific pneumococcal OPA titer for each of the 21 serotypes	V01 and V02 - all participants	OPA GMT and 95% CI, corresponding Forest Plot
	V01 and V02 - 50-64 years	
	V01 and V02 - 65-84 years	
	V02/V01 - all participants	OPA GMT ratio (post/pre) and 95% CI
	V02/V01 - 50-64 years	
	V02/V01 - 65-84 years	
	V02/V01 - all participants	Percentage of participants with titers at V02 \geq 2/4/8/16-fold rise over V01 and 95% CI and <LLOQ at V01 to \geq LLOQ at V02
	V02/V01 - 50-64 years	
	V02/V01 - 65-84 years	
	V02 - all participants	OPA GMT ratio and 95% CI and corresponding Forest Plot between:
	V02 - 50-64 years	
 - each SP0202 formulation (ie, SP0202-VI/SP0202-IIb, SP0202-VII/SP0202-IIb, SP0202-VII/SP0202-VI) - any SP0202 group and Prevnar 13 or Pneumovax 23 (ie, SP0202-IIb/Prevnar 13, SP0202-VI/Prevnar 13, SP0202-VII/Prevnar 13; SP0202-IIb/Pneumovax 23, SP0202-VI/Pneumovax 23, SP0202-VII/Pneumovax 23)
	V02 - 65-84 years	
	V01 and V02 - all participants	OPA titer RCDC
	V01 and V02 - 50-64 years	

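### Values above ULOQ are analysed as if exactly ULOQ, so any true between-group GMT/GMC ratio other than 1 is pulled toward 1 with a shorter interval; a ULOQ count and a censored sensitivity ratio would be a cheap improvement

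*Protocol*

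**What the plan says.** **Upper limit.** Protocol 9.4.3: "Any value reported as > ULOQ (upper limit of quantitation) will be converted to ULOQ". In SAP 4.3.2.1, for a value at or above ULOQ, "then the computed value is ULOQ". The protocol's strict and the SAP's non-strict inequality give the same computed value.

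**Lower limit.** For GMTs/GMCs, protocol 9.4.3 says "any pre-vaccination or post-vaccination value reported as < LLOQ will be converted to a value of 0.5 LLOQ"; the SAP agrees: "If a value is < LLOQ, then the computed value is LLOQ/2".

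**Use of these values.** Protocol 9.4.1 proceeds by "assuming that log10 transformation of the titers / concentrations and titers / concentrations ratio follows a normal distribution", and the interval for a ratio between two groups "will be computed from the difference of log 10 transformed means of titers/concentrations using normal approximation". SAP Table 5.2 then plans, for each serotype at V02, "OPA GMT ratio and 95% CI and corresponding Forest Plot between" the three SP0202 formulations pairwise and each formulation against the two controls, overall and by age group, with the same for IgG.

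**What else is planned.** SAP 5.5.2 only refers back to the substitution rules. The cLDA model in SAP 5.4.4 is described as a baseline adjustment, with no mention of censoring. SAP Table 4.3 with 5.4.3 gives the number and percentage at or above LLOQ. RCDCs, boxplots and quartiles are also planned. Neither document describes a count at or above ULOQ, a re-dilution step or a censored-data analysis.

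**The concern.** A result above ULOQ says only that the titer is at least ULOQ. Entering it as exactly ULOQ removes the upper tail, and removes more of it from the arm with the higher titers. The difference in log10 means therefore shrinks, and so does the SD that sets the interval width: the interval gets shorter as information is lost.

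Protocol 2.1 says the three formulations were developed to help identify a lead for Phase III, and they differ in antigen content for a few serotypes. The study tests no hypotheses, so the estimates and intervals are the whole result. If many sera reach ULOQ for a serotype, a real advantage of one formulation would be displayed as smaller than it is, with an interval tighter than the precision table in protocol 9.2 implies.

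**Working it through.** **Inputs from the documents.** Protocol 9.2: "Assuming a drop-out rate of approximatively 15%, a total of 128 participants by vaccine group" (150 × 0.85 = 127.5), with log10 SDs from 0.5 to 1.0. Substitution rules and interval method as above.

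**Assumptions, because the documents are silent.** Normal log10 values with equal SD in both arms, a true ratio (mainly 2), and a range of shares beyond each limit in the lower arm.

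**Step 1: the plan's own figures.** Single mean, SD 1: 1.96 × 1/√128 = 0.173. Difference of two means, using t with 254 df: 1.969 × √(2/128) = 0.246. At SD 0.7 the difference gives 0.172. All match the table, which assumes uncensored data.

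**Step 2: effect of the ULOQ cap.** For X ~ N(μ, s²) capped at U, let z = (U − μ)/s and q = 1 − Φ(z). The capped mean is μ − s[φ(z) − zq].

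Worked case: s = 0.7, 20% of the lower arm above ULOQ, true ratio 2 (log10 = 0.301).
- Lower arm, μ = 0: z = 0.842, U = 0.589. Shift = −0.7 × (0.280 − 0.842 × 0.20) = −0.078, so the GMT is multiplied by 0.84.
- Higher arm, μ = 0.301: z = (0.589 − 0.301)/0.7 = 0.412, q = 0.34. Shift = −0.7 × (0.367 − 0.412 × 0.34) = −0.159.
- Expected log10 ratio: 0.301 − 0.159 + 0.078 = 0.221 after rounding, a ratio of 1.66.
- The capped SDs are 0.583 and 0.502. SE = √[(0.583² + 0.502²)/128] = 0.068, half-width 0.133 against 0.172 in the plan's table.
- Bias/SE = (0.221 − 0.301)/0.068 = −1.18, so the interval covers the true ratio in about Φ(1.96 − 1.18) = 78% of trials.

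The same calculation over SD 0.5 to 1.0, true ratio 2:

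| Lower arm above ULOQ | Expected ratio | CI width relative to uncensored | Coverage of true ratio |
|---|---|---|---|
| 5% | 1.88-1.91 | 0.92-0.94 | 92-95% |
| 10% | 1.78-1.83 | 0.86-0.89 | 84-94% |
| 20% | 1.63-1.69 | 0.75-0.80 | 52-89% |
| 30% | 1.50-1.56 | 0.66-0.71 | 15-77% |
| 50% | 1.30-1.36 | 0.49-0.54 | 0-29% |

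At a true ratio of 1 both arms shift equally: there is no bias and coverage stays at 95%, although relative width still falls (0.75 at 30%).

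**Step 3: effect of the LLOQ/2 rule, true ratio 2.**

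| Lower arm below LLOQ | SD 0.5 | SD 0.7 | SD 1.0 |
|---|---|---|---|
| 10% | 2.01 | 1.98 | 1.95 |
| 20% | 1.99 | 1.93 | 1.88 |
| 30% | 1.95 | 1.86 | 1.80 |
| 50% | 1.79 | 1.68 | 1.60 |

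At SD 0.3, outside the plan's range, 20-30% below LLOQ gives 2.10-2.11 with a wider interval (1.08-1.09). The direction of this rule is therefore not fixed.

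**Step 4: does a censored analysis recover the ratio?** Censored-normal maximum likelihood on ULOQ-capped simulated data, 1,500 trials each, 128 per arm (share = lower arm above ULOQ):

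| SD, share, true ratio | Substitution: ratio, SE, coverage | Censored ML: ratio, SE, coverage |
|---|---|---|
| 0.7, 10%, 1.5 | 1.42, 0.078, 94% | 1.50, 0.090, 96% |
| 0.5, 20%, 1.5 | 1.36, 0.049, 85% | 1.51, 0.065, 96% |
| 0.7, 30%, 2 | 1.55, 0.060, 56% | 2.03, 0.096, 96% |
| 0.5, 30%, 2 | 1.50, 0.041, 14% | 2.00, 0.068, 94% |

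It does so when the data are normal with equal SDs, which is how these data were generated.

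**The case against.** **The size is assumed.** No LLOQ, ULOQ or share beyond either appears in the documents. Nothing shows that any serotype reaches 10-20% above ULOQ, and at 5% the effect is small. This stands, and it is why the point is an improvement and not a demonstrated error.

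**Both limits might seem to act alike.** A reader might infer that LLOQ/2 substitution also always attenuates ratios. The arithmetic does not support that: it is near neutral up to about 20% below LLOQ at SD 0.5, and costs about 3% at SD 0.7 (1.93/2 = 0.97). Nor are LLOQ counts missing, since the percentage at or above LLOQ is already planned.

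**The standard errors might seem wrong.** They are not. In simulation the substituted SE matched the empirical SD of the capped estimate (0.049 and 0.049). Coverage of the true ratio falls because bias is combined with a shorter interval.

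**The lead might seem to be chosen on these ratios.** Protocol 2.1 names no criterion, there is no margin or selection rule, and fold-rise percentages, RCDCs and cLDA are also planned. The documents support only that the ratios may inform the choice.

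**A censored estimate might seem fit to replace the planned ratio.** It depends on its model. With 20% of the reference arm above ULOQ and SDs of 0.7 and 0.5, a common-SD censored fit gave 2.19 for a true 2.01 (substitution 1.95). With SDs 0.7 and 0.9 it gave 1.80 for 2.04 (substitution 1.41). With 20%/10% low responders and 30% above ULOQ it gave 3.28 for 2.63 (substitution 1.89). This stands against replacement and against a common SD, but not against showing the estimate alongside.

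**Conclusion.** The point holds for the upper limit, as a cheap improvement. The plan treats values above ULOQ as exact, and nothing planned corrects the ratios for this. Under the plan's own normality assumption any true non-null ratio is pulled toward 1 and its interval is shortened relative to uncensored data. With 128 per arm, SD 0.5 to 1.0 and a true ratio of 2, the effect is small at about 5% of the lower arm above ULOQ and becomes material from about 10-20%. At the lower limit the rule matters mainly from about 30% below LLOQ, depending on SD.

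The actual size in this trial cannot be established from the documents. Because the analysis is descriptive, no type I error or power figure is affected.

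**What to change.** Keep the planned substitution tables and forest plots as the main display, and add two items to the SAP before database lock.

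1. **SAP 5.4.3:** report n (%) at or above ULOQ beside each GMT/GMC. The matching LLOQ figure is already planned.
2. **SAP 5.4.4:** pre-specify a sensitivity analysis of the V02 GMT/GMC ratios by censored log10-normal maximum likelihood (for example SAS PROC LIFEREG), left-censored at LLOQ and right-censored at ULOQ, with a separate SD per arm. Trigger it by serotype and assay, for example when any arm has more than 10% beyond a limit. Apply it to all pairwise ratios of that serotype, so that they stay mutually consistent. Show it alongside the planned ratio.

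**Cost:** SAP wording and slightly more analysis work on data already collected, with no new samples, assays or participants. The sensitivity intervals will be wider. The method relies on normality, and the censored estimate can overshoot if the distribution is skewed or contains low responders, so the SAP should state that caution with the output.
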